#### 10.0 DATA SUBMISSION SCHEDULE

Case report forms with appropriate source documentation will be completed according to the schedule listed in this section.

Case Report Form	Submission Schedule
Original Consent Form	Prior to study activities
Eligibility Form	At time of consent; Prior to surgery
Screening/Baseline	Prior to surgery
Surgery/Post-Op Form	Post-Op (within 12 hours)
Post-Op	Post-Op (30 days (+/- 3 days)
Adverse Event Form	Continuous

\*\* Dispensed on the day of surgery with instruction to take first dose prior to surgery and second dose after surgery.

\*\*\* Plasma sample for PGx will be collected at baseline visit. Plasma sample for ZNS level, PGx, electrolyte panel, BUN, Cr, ALT, and AST will be collected within 12 hours after first dose.

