#### 4.0 STUDY DESIGN

This study is a randomized, double-blinded placebo-control trial with three parallel groups, to make use of a common control group. Subjects will be randomized in a balanced fashion into one of 3 arms: ZNS 100 mg pre-op, Placebo, or ZNS 100 mg post-op.

The primary efficacy endpoint will be the proportion of PTS-positive subjects defined as the ratio of PTS-positive subjects to total number of subjects within each study arm/group. Subjects defined as PTS-positive will demonstrate an increase in threshold that is ≥10 dB HL at any frequency from 2-6 kHz post-surgery as compared to baseline audiogram.

The secondary efficacy outcome measures will be: (1) the proportion of PTS-positive subjects as defined above, but the definition of PTS will also include the NIOSH red

flag guideline for permanent threshold shift: an increase in hearing threshold level of 15 dB or more at any frequency (2, 3, 4, 6 kHz). (2) The rate of temporary cochlear change as measured by a DPOAE amplitude shift at any frequency that is significantly greater than the stability of each measurement (i.e., 95% confidence interval of each measurement do not overlap). The rate of DPOAE shift is the ratio of DPOAE shift-positive subjects to total subjects within each arm.

To ensure double-blinding of the trial, each subject will be randomized to one of three treatment arms via an interactive randomization tool (IRT) and assigned to study group. Once randomized, each subject will be provided a kit on the day of surgery that contains two bottles, with one package labeled to be taken prior to surgery and another package designated to be taken within 12 hours after surgery or when the patient is released clinically to oral medication. For subjects randomized to "ZNS pre-op", the pre-op package will contain one ZNS capsule (100 mg PO) and the post-op package will contain one placebo capsule that looks, smells, and tastes the same as ZNS capsules. For subjects randomized to "ZNS post-op", the pre-op package will contain one placebo capsule and the post-op package will contain one ZNS capsule (100 mg PO). For the subjects randomized to "placebo", both pre- and post-op packages will contain placebo.

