## 5.5 Follow-Up Assessments

The follow-up assessments will occur after surgery and include the following tests or procedures:

- 1. DPOAE testing in recovery, within 8 hours after surgery.
- 2. Blood samples taken within 12 hours following the first pill for PGx surveys.
- 3. Collection of laboratory test results for research purposes that include an electrolyte panel, BUN, Cr, ALT, and AST. If these tests are not performed as part of clinical care post-operatively, we will obtain them for research purposes at the time of the PGx blood draw.
- 4. DPOAE, Audiogram, ECochG, and WIN testing 30 days (+/-3 days) after surgery.
- 5. Completion of the Hearing History and Occupation Exposure questionnaire 30 days (+/- 3 days) after surgery.
- 6. Documentation of adverse events.

Follow-up assessments will be planned at the stated time points; actual follow up times may vary due to patient logistics and compliance.

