#### 5.6 Blood collection, transportation, and storage

Blood samples will be collected from each participant during the baseline visit and the post-surgery visit within 12 hours after the pre-operative drug dose. A post-operative nurse will draw blood into a red-top tube (EDTA or citrate) using an IV line. Samples will be labeled with a study identification number. They will be stored in a 2-8°C degree refrigerator at WUSM. Samples will then be transported weekly by a study team member for extraction and stored in a -80°C freezer at Gateway Biotechnology's lab.

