2.7 Sample Size Determination for The Primary Efficacy Outcome Measure

The primary efficacy outcome will be the proportion of PTS positive subjects defined as the ratio of PTS-positive subjects to total number of subjects in each study arm/group. Using pilot data from a retrospective chart review of 75 similar patients undergoing \geq 1-hour drill noise exposure, we estimate the proportion of PTS positive subjects in the placebo group will be 50%. We hypothesize that the expected effect of ZNS either pre-op or post-op will be a 50% reduction of the proportion of subjects with PTS positive as compared to placebo group. This is the desired clinically significant effect for treating hearing loss for single dose of 100 mg ZNS.

The sample size for this study was calculated for the planned comparisons of each of the ZNS groups with the placebo group using a balanced design and a one-sided alpha level of 0.0125 Based on the data from our retrospective study, using Fisher's exact test we estimated that 78 subjects in the ZNS group and 78 subjects in the placebo group will be needed to provide us with 80.4 % power to detect a 50% reduction in the proportion of PTS positive subjects *(from 50% to*

^{**}Dispensed on the day of surgery with instruction to take first dose prior to surgery and second dose after surgery.

^{***} Plasma sample for PGx will be collected at baseline visit. Plasma sample for ZNS level and PGx, electrolyte panel, BUN, Cr, ALT, and AST will be collected 12 hours after first dose.

25% corresponding to an absolute proportion difference of 25%) at the 1-sided alpha level of 0.0125 for each ZNS-Placebo group comparison. A total of 234 subjects will be enrolled to be randomized in this study. All efforts will be made minimize and eliminate drop outs. Given the short term-follow-up of study subjects in a period where they are under medical care, few, if any, drop-outs or lost to follow-up are expected.

Sample size calculations were carried out using PROC POWER procedure in SAS 9.4.

3 Study Outcomes

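### The only post-dose ZNS level is timed from capsule one, which is placebo in the post-op arm, so a compliant draw there can precede any ZNS

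*Protocol*

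**What the plan says.** A ZNS plasma level is timed in two places. The Protocol 9.0 calendar footnote reads "Plasma sample for ZNS level, PGx, electrolyte panel, BUN, Cr, ALT, and AST will be collected within 12 hours after first dose". The SAP 2.6 footnote reads "Plasma sample for ZNS level and PGx, electrolyte panel, BUN, Cr, ALT, and AST will be collected 12 hours after first dose".

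The Protocol text on the same draw agrees on the anchor:

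- Section 5.5 opens with "The follow-up assessments will occur after surgery and include the following tests or procedures" and lists "Blood samples taken within 12 hours following the first pill for PGx surveys". If clinical care has not supplied the post-operative chemistry, "we will obtain them for research purposes at the time of the PGx blood draw".
- Section 5.6 says "Blood samples will be collected from each participant during the baseline visit and the post-surgery visit within 12 hours after the pre-operative drug dose", and then "A post-operative nurse will draw blood into a red-top tube (EDTA or citrate) using an IV line".

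For the post-op arm, Protocol 4.0 says "the pre-op package will contain one placebo capsule and the post-op package will contain one ZNS capsule (100 mg PO". Under Protocol 5.2, capsule two is due up to 12 h after surgery or when the patient may take oral medication.

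In both calendar grids the post-operative blood draw and the second oral dose sit in one column with a 12-hour heading. Neither grid has a draw at day 30.

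The level is used in the pharmacogenetics analysis. Protocol 12.5 screens drug concentration as a possible confounder. SAP 7.1.3 uses it as a variable and names it in one adjustment list. Protocol 2.2 places the genetic work among the secondary objectives; SAP 2.2.3 calls it exploratory.

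**The concern.** A drug level is informative only if the time since the drug was taken is known and is positive. Here the clock starts at a capsule that holds no drug in one of the two active arms. A post-op-arm subject sampled after surgery but before capsule two would have no study ZNS in the sample, and would be recorded as having a post-dose level. In the pharmacogenetics models that value would stand for exposure in someone who later received 100 mg. It would reflect the order of two bedside events, not metabolism.

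The error is tied to arm. In the pre-op arm any draw after capsule one follows ZNS, and in the placebo arm there is no ZNS to miss. With one post-dose draw per subject, no second sample can correct it.

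A smaller issue concerns SAP 8.1.1, which calls for laboratory tests within 12 hours post dose without saying which dose. A normal research sample drawn before capsule two could be counted as a post-dose check.

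**Working it through.** The plan gives no figure to reproduce; the question is whether the permitted windows overlap.

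**Which capsule is the first dose?** The neighbouring footnote in each calendar describes the first dose as the one taken before surgery, and Protocol 5.6 counts from the pre-operative dose. It cannot mean the first dose of ZNS.

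**Inputs.** Let t = 0 be capsule one and S the hours from capsule one to the end of surgery. S is not documented. The only floor is the 45 minutes of drilling in Protocol 3.1, so S ≥ 45/60 = 0.75 h. The values 3, 6 and 9 h below are assumptions.

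**Windows**

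- Capsule two: from S to S + 12, or later if oral medication is not yet allowed.
- Draw, Protocol 5.5, 5.6 and 9.0 footnote: from S to 12, a length of 12 − S.
- Draw, SAP 2.6 footnote: at t = 12. This precedes ZNS if capsule two comes more than 12 − S hours after surgery. The part of the 12-hour capsule-two window lying beyond that point is S/12.
- Draw, calendar column read alone: from S to S + 12, the same window as capsule two, with no order between them.

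| S (h) | 12 − S (h) | S/12 |
|---|---|---|
| 0.75 (floor) | 11.25 | 6.25% |
| 3 (assumed) | 9 | 25% |
| 6 (assumed) | 6 | 50% |
| 9 (assumed) | 3 | 75% |

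The last column is a share of clock time, not of subjects.

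**Example, S = 6 h (assumed)**

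- Capsule two 4 h after surgery (t = 10). Protocol text: draws from t = 6 to 10 precede ZNS, 4 of the 6 permitted hours. SAP footnote: the draw at t = 12 is 2 h after ZNS.
- Capsule two 8 h after surgery (t = 14). Protocol text and SAP footnote: every permitted draw (t = 6 to 12, or t = 12) precedes ZNS. Calendar column: the window is t = 6 to 18, of which 14 − 6 = 8 h precede ZNS and 18 − 14 = 4 h follow it.

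If capsule two is taken as soon as surgery ends, the pre-ZNS interval shrinks to almost nothing. Otherwise a pre-ZNS draw complies with the Protocol text and with the calendar column. The SAP's fixed 12 hours makes it less likely but does not exclude it.

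**The case against.** The strongest reply is that the calendar column lets a site draw up to 12 h after surgery, and so after capsule two. This is a fair reading of the grid, and it matters. A reader might infer from the footnotes alone that no compliant draw exists when S exceeds 12 h, or that every compliant draw precedes ZNS when capsule two is late. Neither statement holds if the column governs. But the footnotes and Protocol 5.5 and 5.6 are more specific than a column heading, and the column does not order the draw and the capsule either. The gap remains on each reading.

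A second reply is that the hours are mostly assumed. That is right. A reader might also be tempted to spread both times evenly over their windows, which gives a pre-ZNS probability of 1 − (12 − S)/24: about 58%, 75% and 92% for S of 2, 6 and 10 h. The documents do not support such a claim. They give neither S nor any distribution of draw or capsule times.

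Third, the samples may already be identifiable. SAP 6.5 lists dose administration, and SAP 10.1.5.3 sorts listings by collection time. This suggests that the clock times may exist, but no rule tells the analyst to use them.

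Fourth, the safety side is slight. SAP 12.1 and 12.2 plan only screening biochemistry, research tests fill in only where clinical care has none, and Protocol 8.0 follows adverse events for two weeks and at the 30-day visit. This reply stands: what is left is an operational notification to the investigator.

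**Conclusion.** The point holds as a possibility written into the plan: a post-op-arm draw can comply and still precede any ZNS, and its level would be analysed as drug concentration. That rests on the text alone. The frequency among the 78 planned post-op subjects is unknown and depends on S, on when capsule two is taken, and on when the nurse draws.

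The damage is confined to one variable in the pharmacogenetics analysis, with a minor effect on the laboratory check. A reader might infer that the efficacy result or the genetic data are compromised. They are not: the primary endpoint and the interim rule use audiograms, and a genotype does not depend on when ZNS was taken. Nor does it follow that post-op-arm levels are useless, since those drawn after capsule two can be used once their timing is known. This is a low-priority correction, worth making because it is cheap.

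**What to change.** In SAP 7.1.3, add one paragraph. After unblinding:

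1. Derive the time from the ZNS-containing capsule to the draw, from the clock times of both capsules and the sample.
2. Flag post-op-arm samples drawn before capsule two as pre-ZNS, and set their drug concentration to missing.
3. Report the number flagged by arm.
4. Account for time since ZNS in the remaining levels.

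The paragraph should also say how the missing concentrations are handled. By the S/12 result, flagging is likelier when surgery is long. Long surgery may go with longer noise exposure, which is in the same models, so dropping these subjects may be selective.

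In SAP 8.1.1, state that a flagged research sample does not count as a post-dose laboratory result. Align the Protocol 9.0 and SAP 2.6 footnotes on one draw time.

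The cost is a short SAP amendment and one derived variable. The case report forms are not in the documents, so the three clock times may or may not already be recorded.

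Moving the draw after capsule two for future subjects, in all arms to keep the blind, is optional. It would reduce pre-ZNS samples, but it may need a new needle stick once the IV line is out, lengthens the interval since ZNS in the pre-op arm, leaves the two active arms sampled at different times since ZNS, and mixes two schedules within the trial. That trade-off is for the sponsor to weigh.

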#### 11.0 DATA AND SAFETY MONITORING

In compliance with the Washington University Institutional Data and Safety Monitoring Plan, an independent Data and Safety Monitoring Board (DSMB) will be specifically convened for this trial to review toxicity data. A DSMB will consist of no fewer than 3 members including 2 clinical investigators and a biostatistician. Individuals invited to serve on the DSMB will disclose any potential conflicts of interest to the trial principal investigator and/or appropriate university officials, in accordance with institution policies. Potential conflicts that develop during a trial or a member's tenure on a DSMB must also be disclosed.

The DSM report for the DSMB will be prepared by the study team with assistance from the study statistician, will be reviewed by the DSMB, and will be submitted to the PI. The DSM report will be prepared for the DSMB semi-annually and at other times at the discretion of the DSMB. The DSMB must meet at least every six months beginning six months after enrollment of the first participant at the secondary site, no more than one month prior to the due date of the DSM report to the PI. This report will include:

- HRPO protocol number, protocol title, Principal Investigator name, data coordinator name, regulatory coordinator name, and statistician
- Date of initial HRPO approval, date of most recent consent HRPO approval/revision, date of HRPO expiration, date of most recent QA audit, study status, and phase of study
- History of study including summary of substantive amendments; summary of accrual suspensions including start/stop dates and reason; and summary of protocol exceptions, error, or breach of confidentiality including start/stop dates and reason
- Study-wide target accrual and study-wide actual accrual
- Protocol activation date at each participating site
- Average rate of accrual observed in year 1, year 2, and subsequent years at each participating site
- Expected accrual end date, accrual by site, and accrual by cohort
- Objectives of protocol with supporting data and list the number of participants who have met each objective
- Measures of efficacy
- Early stopping rules with supporting data and list the number of participants who have met the early stopping rules
- Power analysis and/or interim analysis (if described in the protocol)
- Summary of toxicities
- Abstract submissions/publications
- Summary of any recent literature that may affect the safety or ethics of the study

The study principal investigator and coordinator will monitor for serious toxicities on an ongoing basis. Once the principal investigator or coordinator becomes aware of an adverse event, the AE will be reported to the HRPO according to institutional guidelines (please refer to Section 1.0).

#### 11.1 Adverse Event Collection in the Case Report Forms

All adverse events that occur beginning with start of treatment must be captured in the AE Form.

#### 12.0 STATISTICAL CONSIDERATIONS

## 12.1 Data Analysis

Data will be analyzed using an intention-to-treat principle with patients analyzed in the groups they were randomized to. The primary outcome measure for assessing effectiveness of ZNS (100 mg PO) pre-op will be the proportion of subjects in the pre-op arm experiencing PTS as compared to the control group. The primary outcome measure for assessing effectiveness of post-op ZNS (100 mg PO) will be the proportion of subjects in the "post-op" arm experiencing PTS as compared to the control group. The secondary outcome measures are key audiological and clinical assessments of hearing loss. OAE shift will be a secondary outcome measure and an early indicator of changes in cochlear health and PTS.

Standard descriptive statistics will be used to describe distribution of demographic, clinical and audiometric characteristics as well as outcome measures for each study group. For continuous level characteristics Q-Q plots and Shapiro-Wilk test will be used to test assumption of normality. For normally distributed data, mean and standard deviation will be used as descriptive stats of continuous level variables, and if the assumption of normality is violated we will report median and range for description of variables. Frequency and relative frequency will be used for description of categorical level variables.

#### 12.2 Efficacy analysis

#### 12.2.1 Analysis of primary outcome variable

#### Efficacy analysis at the end of the study

The primary outcome measure for assessing effectiveness of ZNS (100 mg PO) either pre-op or post-op compared to the placebo group will be the proportion of subjects defined as PTS positive 30 days (+/-3 days) after surgery.

Audiogram will be performed to look for PTS. Patients for whom the difference at any frequency from 2-6 kHz in hearing thresholds (30 days ( $\pm$ -3 days) post-surgery - Baseline) is  $\geq$ 10 dB HL will be defined as PTS

positive. Primary analysis and sensitivity analyses will be carried out on the primary endpoint.

#### Primary analysis.

Frequency and relative frequency will be used to describe the distribution of the primary outcome measure in each study group. To assess efficacy, Fisher's exact test will be used to compare the proportion of subjects with PTS positive in ZNS group with the proportion of patients with PTS positive in the placebo group.

To provide an estimate of treatment effect a supportive logistic regression analysis will be done with covariates: age, pre-op hearing dichotomized to normal to minimal hearing loss and slight to mild loss, noise exposure history dichotomized to high risk and low risk, exposure categorized as low (8-hour equivalent A-weighted sound level in decibel (LAeq8hr) < 80 dBA), moderate (LAeq8hr > 80 dBA but < 90 dBA), or high (LAeq8hr > 90 dBA).

#### Sensitivity analysis of the primary endpoint

The potential impact of missing primary endpoint data will be explored in sensitivity analyses using multiple imputation. Two sensitivity analyses performed:

Sensitivity 1: MI analysis under the missing not at random assumption (MNAR)

Sensitivity 2: Logistic regression tipping point analysis under the assumption of data missing at random.

#### Sensitivity 1.

Proc MI procedure in SAS will be used to impute missing data for study treatment groups using the distribution implied by the non-missing patient data within the placebo group. The SAS code to impute data for Sensitivity analysis 1 under the MNAR assumption will be of the form:

```
PROC MI DATA=X SEED=<value> NIMPUTE=10 OUT=MI_OUT1 NOPRINT;
CLASS GROUP;
VAR AGE PTA LSurg......;
FCS LOGISTIC(PTS);
RUN;
```

Post imputation each of the imputed 10 datasets will be analyzed using the same approach as for the primary outcome measure. The estimates of the analysis of the 10 imputed datasets will be then combined following Rubin's rules using PROC MIANALYZE procedure in SAS which will be of the form:

```
PROC MIANALYZE PARMS=GMPARMS COVB=GMCOVB PARMINFO=GMPINFO WCOV
BCOV

TCOV; / *dataset "gmparms" contains the estimates and
associated standard errors for the mean parameters from each of
the M=10 imputed data sets.
dataset "gmcovb" contains the asymptotic covariance matrics
dataset "gmpinfo" contains parameter info*/

MODELEFFECTS INTERCEPT AGE PTA LSurg......;
RUN;
```

#### Sensitivity 2.

Multiple imputation will be used to impute data in each of the study groups. A progressive penalty of  $\delta_i = k_i \times \log{(OR)}$  will be added to imputed values in ZNS arm where (i) OR is the Odds ratio estimate for ZNS as compared to Placebo from the primary logistic regression analysis and (ii)  $k_i = 1, 0.95, 0.90, ... 0.05, 0, 1.05, 1.10,...$  thus k ranges from 1 (equivalent to MI approach based on MAR) to 0 (or higher), until the conclusion of the primary analysis is overturned (i.e., p<0.05 is lost at, this value of  $k_i$  being the 'tipping point'). Rubin's method will be used to combine the primary endpoint treatment effects across imputations for each value,  $k_i$ , of the penalty. Forest plots will be used to graphically display the penalty value that results in loss of statistical significance.

```
SAS code sample for Sensitivity analysis is provided below:
**Step 1: Generate 10 datasets by imputing the missing data**;
PROC MI DATA=X SEED=<value> NIMPUTE=10 OUT=MI OUT1 NOPRINT;
CLASS GROUP;
VAR AGE PTA LSurg.....;
FCS LOGISTIC(PTS);
**Step 2: Generate 10 complete datasets from the 10 monotonized
datasetsin Step 1 for missing values in the drug arm,
subtract DELTA derived above from their imputed data.**;
proc mi data=YYY NIMPUTE=1 SEED=<value> OUT=YYY shift;
by group;
class group;
var AGE PTA LSurg.....;
monotone method=logistic;
mnar adjust(PTS / shift=DELTA adjustobs=(group='1'));
**Step 3: Apply the primary MMRM to the 10 complete datasets in S
tep 2**;
proc genmod data=YYY shift descending;
by imputation ;
class group;
model PTS = group AGE PTA LSurg......;
ods output GEEModPEst=gmparms;
run:
```

```
**Step 4: Obtain the pooled inference from 10 sets of estimates
from Step 3**;

PROC MIANALYZE PARMS=GMPARMS COVB=GMCOVB PARMINFO=GMPINFO WCOV
BCOV
        TCOV;
        MODELEFFECTS group;
RUN;
```

